4.2 Step 2 - Secondary Genetic Counseling Substudy Registration

Select Participating Institutions: Please see Section [4.2.3.2](#) for detailed information and instructions on how to express interest in participation.

4.2.1 Patient Registration Information:

4.2.1.1 Protocol Number

EAQ152

4.2.1.2 Investigator Identification

- Institution and affiliate name
- Investigator's name

4.2.1.3 Patient Identification

- Patient's initials (first and last)
- Patient's Hospital ID and/or Social Security number
- Patient demographics
- Gender
- Birth date (mm/yyyy)
- Race
- Ethnicity
- Nine-digit ZIP code
- Method of payment
- Country of residence

4.2.2 Eligibility Verification

Patients must meet all of the eligibility requirements listed in Section [3.2](#).

4.2.3 Additional Requirements

4.2.3.1 Patients must provide a signed and dated, written informed consent form.

NOTE: Copies of the consent are not collected by the ECOG-ACRIN Operations Office – Boston.

4.2.3.2 To participate in the Genetic Counseling Substudy, sites must contact the study team.

- The designated CRA must send an e-mail to [contact] with the following information:
 - First and Last Name(s) of the Designated Contact(s) at your Institution
 - E-mail address(es) for Designated Contact(s)
 - Site Name
 - CTEP Site ID
 - Street Address
 - City, State, Zip

NOTE: The person(s) identified as the Designated Contact(s) will be responsible for data entry in Rave in the event that the site participates.

All interested sites will be considered for participation in the substudy. Participation will require licensure assessment and licensure of the study team's genetic counselors (at the University of Pennsylvania), per state laws. Participation also requires a designated CRA to assist with testing requisitions, scheduling of remote counseling

Rev. 7/17

4.2.3.3 For patients consented to the COMET Secondary Genetic Counseling Substudy, the responsible/designated CRA must fax the MATCH or other molecular profiling screening results report to the study team ([contact]), and discuss the results with the study team, including the genetic counselors at the University of Pennsylvania, over [contact] Data collection for this study will be done through the Medidata Rave clinical data management system and the EASEE-PRO system. Please refer to Section [4.1.4.3](#) above for Rave access information.

Rev. 2/17

4.2.3.5 EASEE-PRO System:

Please refer to Section [4.1.4.4](#) above with the following modification: Participants who do not have internet access/e-mail may still participate in the Step 2 Genetic Counseling sub-study. For these participants only, site CRAs will need to complete a participant contact form and fax it to the OEAU so that the participant account can be activated manually within EASEE-PRO.

Rev. 7/17

4.2.3.6 Registration of a patient to the COMET Ancillary Study Protocol does not relieve the registering investigator from adhering to correlative study requirements specific for the MATCH or other molecular profiling protocol and not specified by this ancillary protocol.

4.3 Instructions for Patients who Do Not Complete Baseline Survey and/or Do Not Start Assigned Study Intervention

If a patient is randomized in the Primary Intervention Study (Step 1) but the baseline survey (T0) is not completed, patient is considered off study and no additional data will be requested and patients will not be available to register to the Secondary Genetic Counseling Substudy (Step 2).

Patients registered to Step 1 and further registered to Step 2, but who do not proceed with the genetic counseling, are to complete the requirements for Step 1. Specifically, Step 1 follow-up data will still be collected and must be submitted through Medidata Rave and the EASEE-PRO System according to the schedule in the **EAQ152** Forms Completion Guidelines.

For Step 2 participants, if the patient does not complete the baseline survey (T0SS) for Step 2, patient is considered off the substudy and no additional data will be requested for Step 2.

5. Methodology

5.1 Randomization

5.1.1 Primary Intervention Study - RCT of Web-based Pre-disclosure Genetic Education v. Usual Care (Step 1):

We will use a permuted block design for the randomization scheme. We will have 1:1 randomization between arms.

5.1.2 Secondary Genetic Counseling Substudy - Genetic Counseling for Incidental Germline Findings (Step 2):

Single arm pilot study (no randomization)

5.2 Interventions

Rev. 2/17
Rev. 7/17

5.2.1 Primary Intervention Study (RCT) (Step 1):

As shown in the study schema, participants will be randomly assigned to web-based genetic education or a control group receiving usual care.

- Genetic education website (Arm A – intervention group):

Upon completion of the baseline survey, Arm A participants will receive an access code to enter and complete the online education module. Adapted for COMET participants from the COMET pilot study materials, the module is designed to provide information on what can be learned through tumor testing, including the differences between genetic tumor changes and potential germline findings, and next steps including confirmation testing should a germline mutation be suspected. The module, which will be content and usability tested with patients of varied background and cancer diagnosis, features simple text, graphic, and video components.

Arm A participants will be offered access to the web-based genetic education module at the study site following completion of the baseline survey, and will be able to revisit the site using any computer with web access, including a smart phone.

- Usual care (Arm B - control group):

Participants in the usual care arm will not initially have access to the web-based genetic education. Rather their education will be consistent with usual care including conversations with the treating physicians, interaction with and information from clinical and/or MATCH research staff and any additional information they seek out through usual resources. This is intended as a “real world” comparison group. All usual care arm participants will be provided access to on-line genetic web education three months after receiving their tumor genetic testing results. These patients will be e-mailed a link to the website and a code to access the materials, which are viewable on any web-enabled device.

- Both Arms (A & B):

Patients on both Arms A and B will be asked to complete a total of four surveys electronically (see Section 0). A baseline survey (T0) will be administered immediately following registration to COMET. A second survey (T1) will be administered following the intervention/usual care. An electronic link to the T1 survey will be emailed to all patients at 7 days following completion of the baseline survey (T0). A third survey (T2) will be sent to all patients within three days following their receipt of their tumor profile results. An electronic link to a fourth survey (T3) will be emailed to all patients three months following receipt of tumor profile results.

All patients will receive periodic email reminders to complete surveys.

We will coordinate COMET study activities closely with MATCH or other tumor profile procedures to ensure that surveys do not alter the treatment schedule. If participants have not completed surveys, this will not prevent next steps in their care or other tumor profile activities.

We will test surveys and assess burden and completion rates. If there is evidence of burden, we will revisit length and prioritize outcomes and constructs of interest.

Rev. 2/17

5.2.2 Secondary Genetic Counseling Substudy (Step 2 – Arm D and Arm E):

As shown in the study schema, all participants who meet inclusion criteria and criteria for a potential germline mutation identified with molecular tumor profiling at a participating substudy site will be offered the study (up to accrual of 100 patients).

- Genetic Counseling:

Patients who meet criteria for the remote counseling substudy will complete remote counseling visits and surveys as outlined in the study schema. Visit 1 will be standard pre-test counseling; if patients agree to confirmatory germline testing, Visit 2 will consist of result disclosure and review of implications for relatives, consistent with clinical standards in the field. Genetic counselors will be licensed to practice (if necessary) in the states where sites reside consistent with state laws. Similar to our other remote counseling studies, standardized counseling checklists will be utilized by genetic counselors to ensure fidelity to the communication protocols^{15,17,18}. All sessions will be audiotaped to evaluate fidelity and to inform potential future modifications for alternative delivery models. Genetic counselors will collaborate with the patient's treating physician as they will be the ordering provider. Thus, test results and recommendations will be communicated to the patient's treating physician and genetic counselors will collaborate with the treating physician as needed. Implications of germline findings for relatives will be communicated to patients, including how relatives can obtain clinical genetic testing.

There will be no genetic counselors providing counseling services in the primary randomized study. A large number of genetic counselors from the PENN cancer genetics team will be involved in development of the web-based genetic education.

For the sub-study, we will utilize genetic counselors from the PENN cancer genetics team, as this pool of counselors has cultivated extensive experience in conducting genetic counseling with advanced cancer patients in the context of tumor profiling.

- Germline Genetic Testing:

All confirmatory germline testing will be completed through a commercial CLIA-approved lab. The genetic counselor will provide recommendations for testing and the treating physician will be the ordering provider for clinical germline testing. The genetic counselor will disclose the genetic test results to patients during Visit 2 and will collaborate with the treating physician to provide recommendations for testing relatives.

- In summary, the Step 2 procedures for both Arm D and Arm E (per Section [6.2](#)) will include the completion of up to 4 surveys and the associated interventions, as listed below:

- All Step 2 participants will complete:
 - a baseline survey (T0SS)
 - a visit with a genetic counselor for germline mutation counseling (GC Visit 1)
 - a post GC Visit 1 survey (T1SS)
- Additionally, if a participant agrees to confirmatory testing, this individual will also have:
 - a second visit (GC Visit 2) with a genetic counselor
 - a post GC Visit 2 survey (T2SS)
 - and a 3 month survey (T3SS)
- For Arm D patients (i.e., those from Step 1 Arm A or Arm B), information taken from T2 (see Sec. 6.1) will be used to pre-populate T0SS, and only the remaining items in T0SS will need to be completed.
- Participants with email access will be directed to complete surveys online. Those without email access may complete paper surveys instead.

Rev. 7/17

Rev. 2/17
Rev. 7/17

5.2.3 Alternative pathway to Substudy (Step 1 - Arm C, then Step 2 – Arm E):

In an effort to reduce the length of time to recruitment and completion of the substudy, we have included an alternative pathway for entry therein.

- As indicated in the study schema, following enrollment in screening for MATCH, a subgroup of patients who receive their tumor molecular profile results (report of any actionable mutations) from their treating physician, and who meet criteria for potential actionable germline mutation (AIM 2), will be consented to the

COMET substudy. These individuals will not be required to complete the main study (Step 1 - Arm A or B) to be eligible for the substudy (Step 2).

- Patients who are eligible and consent to participate in the substudy, and who were not enrolled on either Arm A or Arm B, will be registered to Arm C (Step 1; substudy only). These individuals will not participate in or complete any primary study (Arm A or B) education or surveys.
- Arm C participants will immediately be registered to Arm E (Step 2) and complete all of the Step 2 procedures (per Section [6.2](#)), including the completion of up to 4 surveys and the associated interventions (see Section [5.2.2](#) above). For Arm E patients, the entire T0SS will be completed as the baseline survey.

Rev. 7/17

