If patients still have not responded within 12 days of the original e-mail, the OEAU Research Associate may attempt to telephone the patient and administer the questionnaire over the telephone. If questionnaires are telephone-administered, they will be marked as such in the data base. All surveys, while desired within 3 days of the event, will remain available for participants until either the surveys are completed or they are off-study. Since the completion date is recorded for all surveys, the study team will be able to make relevant determinations for inclusion of this data in specific analyses. However, after telephone follow-up, no additional or extraordinary means will be employed to collect overdue/missing questionnaires.

Only participants on Step 2 without email access may complete paper survey. The timing of administration will be the same as the web-based surveys.

Participants unable to enter their survey responses may designate a “scribe” to relay their responses. Participants will be able to indicate whether the survey was filled in by the participant or the designated scribe.

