As MATCH has approached its goal of sequencing ~6000 patient tumors, this section incorporates changes to expand eligibility criteria (effective since Addendum #3) to allow patients from select sites who potentially undergo tumor profiling through non-MATCH assays and to increase the accrual goal (effective since Addendum #6). In this section, patients who enter COMET through MATCH Step 0 (prior to or after the activation of this addendum allowing for eligibility expansion) will be referred as the MATCH cohort, and other patients (who enter after the corresponding addendum activates) will be referred as the non-MATCH cohort.

7.1 Primary Study: Randomized Study of Web-based Pre-disclosure Genetic Education versus Usual Care (Step 1 – Arms A & B)

Rev. 2/17

NOTE: Patients on Arm C (see Section [□□□□](#)) will not participate in or complete any primary study (Step 1) education or surveys, and will immediately be registered to Arm E and complete all of the substudy (Step 2) procedures.

Rev. 7/17

7.1.1 *Primary endpoints* will include change in knowledge and distress (state anxiety, Promis anxiety, Promis depression and cancer specific distress) from baseline to post-education (T0 to T1) and baseline to post-disclosure (T0 to T2).

The following 10 analyses are of primary interest: change scores from T0 to T1, and T0 to T2 of each of the following five outcomes: knowledge, state anxiety, cancer specific distress, Promis anxiety and Promis depression, which correspond to 10 primary analyses. To account for the 10 primary analyses, A Bonferroni correction is considered here, setting the nominal p-value to declare statistical significance of $p < 0.005$ (5% Typical Type I error rate / 10 comparisons = 0.5% nominal p-value for declaring statistical significance). Preliminary data from the COMET pilot study (State Anxiety, IES-Total, Knowledge) is used to calculate power. As there was no preliminary data for Promis Depression/Anxiety in a similar setting, power calculation for these two measurements are based on data reported in Hinds et al. (2012). A sample size of 200 (with evaluable paired data) /arm is chosen here, which provides at least 85% power for all short-term outcomes (e.g. T0-T1) and changes in knowledge and cancer specific distress after receipt of tumor profiling results (e.g. T0-T2), using t test at two-sided 0.005 significance level.

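### Usual-care patients receive the education website at the same three-month point as the T3 survey, so control T3 answers can follow exposure to the intervention

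*Combined protocol and SAP*

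**What the plan says.** On Arm B, section 5.2.1 says: "All usual care arm participants will be provided access to on-line genetic web education three months after receiving their tumor genetic testing results". The route is e-mail: "These patients will be e-mailed a link to the website and a code to access the materials". No condition is attached to having returned any survey.

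On the surveys, the same section says: "An electronic link to a fourth survey (T3) will be emailed to all patients three months following receipt of tumor profile results". For the survey before it: "A third survey (T2) will be sent to all patients within three days following their receipt of their tumor profile results".

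Section 5.4 sets reminders after 3 working days and a possible telephone attempt after 12 days. It then says that "after telephone follow-up, no additional or extraordinary means will be employed to collect overdue/missing questionnaires". Surveys nevertheless have no closing date; they "will remain available for participants until either the surveys are completed or they are off-study". The provision for late answers is this: "Since the completion date is recorded for all surveys, the study team will be able to make relevant determinations for inclusion of this data". No rule for those determinations is given there or in section 7.1.2.

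Section 7.1.1 defines the primary endpoints as changes "from baseline to post-education (T0 to T1) and baseline to post-disclosure (T0 to T2"). T3 is not among them. It enters the longitudinal GEE models of section 7.1.3, which are labelled exploratory. The moderator analyses, a secondary objective in section 2.2.1, add interaction terms to those same models.

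**The concern.** A randomised comparison at T3 is interpretable only if the controls have not had the intervention when they answer. Here the control arm is handed the intervention on the day its T3 survey falls due, with no stated order between the two e-mails. A control who opens the module first and answers T3 afterwards is still analysed as usual care.

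Two things are at stake. The first is the T3 arm effect. Section 7.1.3 asks whether the arm effect changes over time, and a narrowing at T3 could mean that the effect of education fades or that controls have just caught up. The data as planned would not separate these. The second is the moderator analysis, which uses T3 as one of its follow-up waves.

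Because surveys have no closing date, an unanswered Arm B T2, which does feed primary endpoints, could in principle also be completed after access.

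**Working it through.** **Timeline, counted from receipt of tumor results**

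| Event | Timing | Section |
|---|---|---|
| T2 sent, both arms | day 0 to day 3 | 5.2.1 |
| Website link and code to Arm B | 3 months | 5.2.1 |
| T3 link, both arms | 3 months | 5.2.1 |
| T3 e-mail reminders | from 3 working days after the T3 link | 5.4 |
| T3 telephone attempt possible | from 12 days after the T3 link | 5.4 |
| T2 and T3 close | on completion or off-study | 5.4 |

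**T3.** Scheduled gap between website access and the T3 link: 3 months − 3 months = 0. The plan then pursues T3 answers for at least 12 more days, during which Arm B already holds the code.

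**T2.** Taking three months as about 91 days (my conversion), a T2 sent on day 0 to 3 meets access only if it is answered 88 to 91 days after it was sent. That is 88 − 12 = 76 to 91 − 12 = 79 days after the telephone attempt becomes possible, when active pursuit has ended. An outstanding T1, due before results are returned, would have to be later still.

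**How an exposed survey is analysed.** Section 7.1.2 analyses by randomised arm regardless of crossover, so it counts as usual care. The as-treated repeat classifies patients by the intervention received. It does not say how to treat a control who was unexposed at T1 and T2 and exposed at T3, although every control is offered the website by design.

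**Illustration for the primary T0–T2 change.** I first reproduce the plan's own power at 150 per arm, two-sided 0.005.

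- Evaluable number: 670 × 0.45 / 2 = 150.75 per arm.
- Noncentrality = difference / √((s₁² + s₂²)/n).
- Knowledge: difference 5.86 − 4.40 = 1.46; √((4.30² + 3.05²)/150) = 0.430; 1.46/0.430 = 3.39. Power is 71% by the unequal-variance t and 72% by the normal approximation; the plan states 72%.
- Cancer specific distress (IES-Total): difference −1.00 − (−2.17) = 1.17; √((1.53² + 2.86²)/150) = 0.265; 1.17/0.265 = 4.42. Power is 94% and 95%; the plan states 95%.

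Now let f be the share of analysed Arm B T2 surveys answered after using the website. Assume that those patients gain the full Arm A effect and that the SDs do not change. The difference becomes (1 − f) × planned. The documents give no f.

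| f | Arm B surveys out of 150 | Power, knowledge | Power, IES-Total |
|---|---|---|---|
| 0 | 0 | 71% | 94% |
| 5% | about 8 | 65% | 91% |
| 10% | 15 | 59% | 87% |
| 20% | 30 | 46% | 76% |

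**T3.** The plan gives no expected T3 difference, so there is no power figure to recompute. Under the same assumptions the T3 arm difference is multiplied by (1 − f).

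**The case against.** The strongest reply is that the primary analyses are barely touched. All ten use T1 or T2. The longitudinal models include wave-by-arm interactions, so the T1 and T2 arm effects are estimated separately from T3. T3 is only one follow-up wave in the moderator models. Contamination that moves controls towards Arm A biases towards no difference and does not create a false positive. All of this stands.

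The plan also has means of finding exposed surveys. Completion dates are recorded (5.4), individual website activity is tracked (5.8, although the end of tracking is defined only for MATCH patients), crossover proportions are to be reported (7.1.4), and as-treated repeats are planned (7.1.2, 7.1.3). That stands too, but none of these is tied to a rule for a survey dated after access, and choosing the rule after seeing the data is avoidable.

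The Step 1 schema is a figure not reproduced in the text I have, and the forms schedule is in the Forms Completion Guidelines, which are not included. Either might put T3 first. The protocol text does not.

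A reader might infer that nearly all controls see the module before answering T3. The documents do not support this. They set the same three-month offset for two e-mails and say nothing about which is opened first. Nor do they show that a module written for use before disclosure has its full effect when opened three months afterwards.

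**Conclusion.** The point holds for T3. Access and survey fall due together, the survey stays open, and no rule governs an answer given after access. The likely direction is towards no difference at T3, in the exploratory longitudinal models and in the moderator models serving the secondary objective. The size cannot be derived from the documents, because it depends on how many controls open the module first and how far it then changes their answers.

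A reader might go further and conclude that the primary T0–T2 result is compromised. The documents do not support that. The route needs an Arm B T2 about three months late, after active pursuit has ended. At f = 5%, about 8 of 150 analysed Arm B surveys would have to be both that late and preceded by use of the module. This is probably rare, though no share is given. The power table shows sensitivity under a full-effect assumption and is not a forecast.

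This is a cheap improvement, not a flaw in the primary design.

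**What to change.** **Section 5.2.1.** Release the Arm B access code when T3 is submitted. For non-responders, set a backstop date after the T3 reminder and telephone cycle, so that every control still gets access.

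**Section 7.1.2.** Prespecify completion-date windows for T1, T2 and T3, identical in both arms, using the dates already recorded. End the T2 window before the three-month point and the T3 window no later than the backstop, so that in-window control answers precede access. Add a sensitivity analysis that excludes Arm B surveys dated after website access, and state whether access means first recorded log-in or release of the code.

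Do not close outstanding surveys in Arm B alone when the code is released. Arm A has its code from baseline, so its late surveys would stay open while Arm B's closed. That would create a difference in ascertainment between arms in a trial where T0-and-T2 completion is already about 45%.

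**Cost.** A changed e-mail trigger and a short addition to the analysis plan. Controls who answer T3 promptly wait hardly longer, and non-responders wait until the backstop. A few very late surveys leave the main analysis. Planned sample size, significance level and arms are unchanged.
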